# 7.8 Adverse Event Stopping Guidelines

Based on results from previous vaccinations with 12-MP and tetanus peptide preparations, and with findings from use of resiquimod and polyICLC, significant toxicity is not anticipated. The study will be monitored continuously for treatment-related adverse events within each vaccine preparation by the sponsor. Data from the UVA- Mel44 vaccine trial (Arm A) (using 12-MP and tetanus peptide) indicate an 8% rate of treatment-related unexpected Grade 3 adverse events.

Version Date: 07-31-17

Adverse events will be described and coded based upon the NCI CTCAE v4.03.

A DLT is defined as any unexpected adverse event that is possibly, probably or definitely related and:

- ≥ Grade 3, with the exception of grade 3 injection site reaction with ulceration ≤ 2 cm
- ≥ Grade 1 ocular adverse events as defined under Section 7.5
- ≥ Grade 2 allergic/autoimmune reactions

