Thus far, 10-15% of participants receiving peptide-based vaccines in the studies at UVA were diagnosed with definite vitiligo. In all cases, the vitiligo was asymptomatic. No major visual/ocular toxicity was reported for participants on these prior trials.

Toxicities Previously Reported for Participants Receiving the 12-MP vaccine administered in Montanide ISA-51 adjuvant

Participants have been vaccinated with a mixture of 12 short melanoma peptide mixture, plus tetanus peptide, in Montanide ISA-51 adjuvant (MELITAC 12.1) in 62 participants on the UVA-Mel43 trial, to about 80 participants in the UVA-Mel44 trial, and to about 40 participants on the UVA-Mel48 trial. Toxicity data for the first 102 participants on the Mel43 and Mel44 trials were graded using the NCI Common Terminology Criteria for Adverse Events v3.0 and are listed regardless of attribution. Maximum Grade 2-4 toxicities experienced by at least 10% of participants are listed in Table 3:

Table 3. Toxicities related to administration of MELITAC 12.1 melanoma vaccine administered with Montanide ISA-51 (IFA) in 102 patients on UVA-Mel43 and UVA-Mel44 clinical trials

Toxicity	Grade 2	Grade 3
Fatigue (lethargy, malaise, asthenia)	17%	3%
Injection site reaction	87%	2%
Ulceration	7%	3%

The grading of injection site reactions was modified from CTC v2.0 to CTCAE v3.0, and now to v4.03. CTC v2.0 did not have an ulceration Adverse Event Term, therefore participants with ulceration in conjunction with an injection site reaction were graded as experiencing a Grade 3 injection site reaction (ulceration or necrosis that is severe; operative intervention indicated). In prior UVA HITC studies, an injection site reaction with ulceration ≤ 2 cm in maximal diameter was an expected adverse event in a subset of participants. However, an injection site reaction that included ulceration >2 cm in diameter, or an injection site reaction requiring debridement, narcotic analgesics for pain, or surgery was not an expected toxicity and was considered a dose-limiting toxicity (DLT) and was graded as a Grade 3 injection site reaction. UVA-Mel43 used the CTC v2.0 grading system whereas UVA-Mel44 used the CTCAE v3.0 grading system. In CTCAE v3.0, ulceration is a separate Adverse Event Term;

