therefore, ulceration and injection site reactions can be graded separately. For this study, participants who experience induration at their injection site, both injection site reaction and induration will be graded and reported. The data in Table 3 have been corrected to be consistent with CTCAE v3.0. The criteria for each of these toxicity categories (fatigue, injection site reaction, and ulceration) have changed from v3.0 to v4.03, but are very similar. Thus, they are probably comparable, but the exact details for assessing them in v4.03 require information that was not collected at the time those studies were performed. In the proposed study, we will grade based on v4.03, and we do not expect Grade 3 injection site reactions; ulceration and injection site reaction toxicities will be expected at Grade 2.

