Injection site reaction/induration was experienced at maximum grade 3 in 5% of patients in Arm A of Mel44. Ulceration was experienced as maximum grade 3 in 7% of patients in Arm A of Mel 44. By the rule above (observed in  $\geq$ 5% of treated patients), injection site reaction, induration, and ulceration would be expected at grade 3. Despite this and in the interest of the patients, we would consider grade 3 injection site reaction with significant ulceration of the skin ( $\geq$  2 cm) as a DLT (see section 7.8).

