#### 9.7 Analyses

### 9.7.1 Safety:

All participants who receive any study intervention will be monitored for adverse events. Adverse events will be described and coded based upon the NCI CTCAE v4.03. A DLT is defined as any unexpected adverse event that is possibly, probably or definitely related to treatment and satisfies the criteria in section 7.8. Occurrence of DLTs will guide escalation and stopping decisions. At study conclusion frequency, proportion and severity of adverse events, and DLTs by arm will be tabulated.

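### The DLT definition counted against the Part 2 stopping boundary (Table 21) is inconsistent for vaccine-site ulceration, on expectedness and on grade

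*Combined protocol and SAP*

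**What the plan says.** **Operative definition.** Section 7.8 begins "A DLT is defined as any unexpected adverse event that is possibly, probably or definitely related and" and then lists its criteria. The first is grade 3 or higher, "with the exception of grade 3 injection site reaction with ulceration ≤ 2 cm". Section 9.7.1, in the statistics chapter, repeats the restriction: "A DLT is defined as any unexpected adverse event that is possibly, probably or definitely related to treatment and satisfies the criteria in section 7.8". Section 7.1.2 defines an unexpected event as one not listed in 7.4.3.

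**Expectedness of site events.** Table 7 in 7.4.3 lists skin ulceration and injection site reaction as separate terms under a Grade 2 heading. The text after it applies the section's own rule (seen in at least 5% of treated participants) and concludes that "injection site reaction, induration, and ulceration would be expected at grade 3". It continues "Despite this and in the interest of the patients, we would consider grade 3 injection site reaction with significant ulceration of the skin", with the size printed as ≥ 2 cm, to be a DLT, and refers to 7.8. Section 1.2.7 says of this study that "we do not expect Grade 3 injection site reactions; ulceration and injection site reaction toxicities will be expected at Grade 2". For prior trials, 1.2.7 records that a site reaction with ulceration > 2 cm "was not an expected toxicity and was considered a dose-limiting toxicity (DLT) and was graded as a Grade 3 injection site reaction".

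**Trigger without grade.** Section 5.4.2 calls ulceration > 2 cm a DLT and takes the patient off study. It sets no grade and no expectedness condition.

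**Use of the count.** Section 9.6.2 monitors the number of participants with a DLT against Table 21: at least 2 among 2-4 participants, at least 3 among 5-11, at least 4 among 12-18. Crossing suspends accrual pending review. The same section quotes 1/16 DLTs on Arm E in Part 1.

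**The concern.** A stopping rule needs an event definition that two people applying it to the same patient would read the same way. Here, whether a large vaccine-site ulcer is a DLT depends on which section is opened. Safety of same-site vaccination is a stated Part 2 objective, and 5.4.2 itself provides for severe inflammation or ulceration after repeated injection at one site. The only formal Part 2 boundary counts DLTs and nothing else. Applied literally, 7.8 and 9.7.1 can leave out of the count an event that 7.4.3 and 5.4.2 both call a DLT. A patient could therefore leave treatment for a DLT that is not counted against Table 21.

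**Working it through.** **1. The boundary itself.** Inputs from 9.6.2: p0 = 0.05, p1 = 0.30, type I error 0.05, type II error 0.20. The Wald upper boundary is the smallest integer d with

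d ≥ [ln((1 − 0.20)/0.05) + n·ln(0.95/0.70)] / [ln(0.30/0.05) + ln(0.95/0.70)] = (2.773 + 0.305n)/2.097 = 1.322 + 0.1456n.

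This gives 1.905 at n = 4 (so 2), 2.050 at n = 5 (3), 2.924 at n = 11 (3), 3.069 at n = 12 (4) and 3.943 at n = 18 (4). It matches Table 21 at every n from 2 to 18. The boundary is correct; the open question is what is counted.

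**2. The passages side by side**, for related events:

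| Event | 7.8/9.7.1 with the expectedness statement in 7.4.3 | 7.8/9.7.1 with 1.2.7 | 7.4.3 override | 5.4.2 |
|---|---|---|---|---|
| Grade 3 site reaction, ulceration > 2 cm | not a DLT | DLT | DLT | DLT |
| Ulceration > 2 cm, graded below 3 | not a DLT | not a DLT | not covered | DLT |

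The first row is the expectedness conflict and the second the grade conflict. Whether the second row can occur in practice depends on the CTCAE v4.03 grading criteria, which Appendix 6 links but does not reproduce. There is also a coding gap: the ≤ 2 cm exemption in 7.8 names injection site reaction only. An event coded solely as grade 3 skin ulceration of ≤ 2 cm would fall under the general grade 3 clause without that exemption, if regarded as unexpected.

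**3. Sensitivity of the boundary to one event.** One DLT among the first four participants does not cross; one large ulcer in another participant makes two and does. The same holds for the third event at 5-11 participants and the fourth at 12-18.

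**4. Illustrative crossing probabilities.** Grade 3 ulceration rates in the documents are 2% (Mel58, Table 5), 3% (Mel43/Mel44, Table 3), 6% (Mel44, Table 5) and 7% (7.4.3: "Ulceration was experienced as maximum grade 3 in 7% of patients in Arm A of Mel 44"). Assume that other DLTs occur independently at rate o, that ulcers occur at rate u, and that every grade 3 ulcer counts. Then p = 1 − (1 − o)(1 − u); for example, o = 5% and u = 7% give 1 − 0.95 × 0.93 = 0.1165. Exact binomial recursion over Table 21, checked after each participant from n = 2 to n = 18, gives:

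| Ulcer rate counted | No other DLTs | 5% other DLTs |
|---|---|---|
| 0 (ulcers do not count) | 0% | 2.9% |
| 2% | 0.3% | 6.4% |
| 3% | 0.9% | 8.7% |
| 6% | 4.6% | 17.6% |
| 7% | 6.6% | 21.2% |

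The zero row is the literal reading in which grade 3 ulceration is expected and never counts.

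**The case against.** The strongest reply is that the protocol already answers the question. Section 7.4.3 raises the expectedness problem and overrides it for grade 3 reactions with large ulceration, citing 7.8. The ≤ 2 cm exemption in 7.8 would have no purpose if expectedness already removed all grade 3 site reactions. Table 7's Grade 2 heading, its note that hyperglycemia of grade 3 or higher is not expected although hyperglycemia is listed, the prior-trial convention and 1.2.7 all point the same way. This stands as evidence of intent. A reader might infer from the literal wording that ulcers never count and that the boundary is blind to the main local toxicity of same-site injection; the documents as a whole do not support that. What remains is that the two sections defining the counted event do not carry the override.

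A reader might also take 17.6-21.2% against 2.9% as the size of the problem. That is too strong. It compares the likely reading with the less likely one, treats every historical grade 3 ulcer as > 2 cm, and adds ulcers to a 5% rate that 9.6.2 sets for DLTs overall.

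Oversight limits the harm. The sponsor monitors continuously, and the Data and Safety Monitoring Committee meets monthly and reviews all adverse events and the application of stopping rules. Crossing only suspends accrual for review. But none of this says which definition governs the count.

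Finally, one might infer that the Arm E figure was counted under a different rule, because the change log dates the ≤ 2 cm exception to the 06-26-17 amendment that added Part 2 after Part 1 accrual was complete. Nothing shows that it was, and 1/16 does not enter the boundary calculation. It only needs confirming.

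**Conclusion.** The point holds as an inconsistency of definition that should be fixed. It is not an error in Table 21, and it does not show that large ulcers are excluded from safety monitoring. Confidence is high that the sections conflict on expectedness, since this can be read directly from current text. It is lower for the grade conflict, whose practical effect rests on criteria outside the documents. The numerical effect on the chance of crossing is uncertain. Across the documented ulcer rates it is 0.3 to 6.6 percentage points if there are no other DLTs, and about 3.5 to 18.3 points (6.4 − 2.9 and 21.2 − 2.9) under the assumed 5% of other DLTs. Both ranges are illustrations: the share of ulcers > 2 cm and the rate under same-site injection of this vaccine are not given.

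**What to change.** Reconcile 1.2.7, 5.4.2, 7.4.3, 7.8 and 9.7.1 into one DLT definition. It should state whether the unexpectedness condition and a grade condition apply to vaccine-site events, and which adverse event terms it covers (injection site reaction, skin ulceration, induration). The choice of rule is the sponsor's. Name that definition in 9.6.2 as the one counted for Table 21, and confirm that the Arm E count of 1/16 quoted there used it, or restate the count.

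Two clerical points can be corrected in the same edit: 7.4.3 prints ≥ 2 cm where 5.4.2 has > 2 cm and 7.8 exempts ≤ 2 cm (possibly a typing or PDF error), and 5.5.2.1 points to 7.4 for the DLT definition where other sections point to 7.8.

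The cost is protocol wording in six places and one check of existing data. It needs no new patients, procedures or analyses, and the Table 21 boundary does not change.

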# 7.9 Responsibility

7.9.1 The University of Virginia Cancer Center Data and Safety Monitoring Committee (DSMC) will provide oversight of the conduct of this study. The CC DSMC will report to the UVA Protocol Review Committee (PRC).

7.9.2 The UVA CC DSMC will review the following:

All adverse events

Audit results

Application of study designed stopping/decision rules

Whether the study accrual pattern warrants continuation/action

Protocol violations

7.9.3 The UVA CC DSMC will meet every month for aggregate review of data. Tracking reports of the meetings are available to the PI for review. Issues of immediate concern by the DSMC are brought to the attention of the sponsor (and if appropriate to the PRC and IRB) and a formal response from the sponsor is requested. Per the UVA Cancer Center NIH approved institutional plan, this study will be audited approximately every 6 months.

### 7.10 Endpoint Data

- 7.10.1 Endpoint data will be collected using HITC IML data forms, participant-specific binders, and the HITC laboratory database.
- 7.10.2 The HITC laboratory database, which has password-restricted access, is stored on the UVA Health System Computing Services secure server.

## 8.0 EVALUATION OF IMMUNOLOGIC RESULTS

A primary goal is to evaluate immunogenicity of LPV7 in each of 7 adjuvant preparations, including IFA, with or without TLR agonists. The primary immunological response of interest is the CD8+ T cell response to the defined minimal peptides epitopes contained within each of the 7 long peptides (Table 2). This will be assessed primarily by Elspot assay as outlined below. Associated analyses will include the durable immune response (week 26), and the peak magnitude of the CD8+ T cell responses. Details related to study design are in Section 9.

Studies in the peripheral blood will also assess CD4 T cell responses, T cell persistence, antibody response, Th1/Tc1 deviation and cytokine functionality. The antitumor immune response to vaccination with LPV7 with TLR agonists will be compared to vaccination with

Version Date: 07-31-17

IFA alone, and the highest immune response rate will be selected. Blood will be collected as described in Section 6.

Skin biopsy specimens from the vaccine sites after 1 (day 8) and 3 vaccines (day 22) (and from normal skin controls) will be evaluated for changes induced by TLR agonists, and these will be evaluated as we have for a prior study  $^{50}$ : immunohistochemistry of the vaccine-site immune cells to define the cell types and function; multiparameter flow cytometry to identify activation status of antigen specific cells, regulatory T cells, and MDSC; ELIspot assays for the ability to produce IFN $\gamma$ ; and Luminex studies to define the cytokine and chemokine profiles of the VSME.

The following laboratory criteria will be used to evaluate effects of the vaccines and the TLR agonists in circulating peripheral blood mononuclear cells (PBMC) and in the vaccine sites. In general, immunological evaluations will be performed in batch.

### 8.1 Immunohistochemistry and Immunofluorescence of skin biopsy specimens

For the immunohistochemical studies of the VSME, we will employ stains with single antibodies (eg CD8), with multiple antibodies (eg CD8 and FoxP3), and a technique developed by our colleague [name], which we have working our lab now. This technique, called SIMPLE, enables repeated IHC stains on the same section, with whole-slide imaging using an Aperio or Leica system, and multiparameter evaluation of these cells in situ by combining the multiple images with each antibody. 67 Immunofluorescence studies will also be available in the event they are helpful.

We will obtain CD8/FoxP3 ratios to evaluate whether higher (more favorable) ratios are induced by adjuvants that are associated with improved circulating immune responses.

For optimization of antibodies in IHC, we have used positive control tissues, which will continue to be useful controls in the proposed studies. These include, but are not limited to, normal human peripheral blood lymphocytes (PBL), PBL activated with CD3/CD28 beads (activated PBL), human lymph node tissue from non-melanoma patients (LN), and inflamed human tissue from a surgical specimen of Crohn's disease (Crohn's).

#### 8.2 ELlspot assav

We will evaluate CD4+ and CD8+ T cell responses in the peripheral blood using a direct (ex vivo)  $\Box$  Ispot assay for IFN $\gamma$  as reported. This will be performed in a core laboratory dedicated to immune monitoring, and with SOPs, controls, and quality assurance measures, which we have reported. Vaccination site infiltrating lymphocytes will be evaluated by  $\Box$  Ispot as well. Vaccine site infiltrating lymphocytes will be compared to those in peripheral blood.  $\Box$  Ispot assays after one in vitro stimulation (stimulated  $\Box$  Ispot) may also be employed if appropriate, as reported  $\Box$ 

 $\underline{\text{CD4+ T cell responses}}$  will be assessed by IFNY  $\underline{\text{EL}}$  lspot assay using the mixture of 7 long peptides and also pools of 15-mer peptides (overlapping by 5 residues) from each peptide (4 peptides for each long peptide) as antigen sources.

Durability of CD8 and helper T cell responses will be assessed by measuring T cell activity at 26 weeks, and for longer intervals when available, with the hypothesis that there will be increased durability of T cell responses when compared to prior experience with short peptides and will be improved with TLR agonists when compared to IFA alone in this study.

We have extensive stores of cryopreserved T cells reactive to minimal epitope peptides included in the 12 short peptides (12MP) mixture, and detectable by IFN-gamma ELIspot assay 8;12 and by cytotoxicity assays. These cells will serve as positive controls for reactivity to the minimal epitopes contained within the long peptides used in this trial.

#### 8.3 Tetramer assay and multiparameter flow cytometry

Peripheral blood lymphocytes and VSME lymphocytes will be evaluated by flow cytometry after incubation with MHC-peptide tetramers or pentamers for the number of peptide-reactive T-cells. We have validated tetramers for all 5 of the minimal CD8 epitopes restricted by HLA-A2 or A3 among the LPV7 peptides. We will use these MHC multimers with which we also have substantial experience. Tetramers will likely detect more antigen-specific T cells than are detected in the functional ELIspot assay, but the primary measure of CD8 T cell response will be the ELIspot assay, on which the statistical power was based. Tetramers will also be used in multiparameter flow cytometry to determine the effector/memory status of the antigen-specific T cells (CD45RA, CD27, CD28, CCR7, CD62L), and evaluation for multiple functions of the CD8 T cells (degranulation (CD107a), IFNy, MIP-1 $\beta$ , TNF $\alpha$ , and IL-2) T1

We will also use multiparameter flow cytometry to measure myeloid suppressor cells (CD14+ HLA-DR lo/neg), and several subtypes of MDSC in PBMC to determine if they are increased or decreased by any of these vaccine approaches, compared to our current experience with MDSC numbers using our short 12MP vaccine (data not shown).

### 8.4 Proliferation assay / Cytokine Analysis

To characterize responding T cells more completely, we will evaluate with multiparameter flow cytometry after short-term culture with antigen. CD4 $^+$  T cells responding to antigen by CFSE dilution will be assayed for intracellular cytokine production to evaluate Th1/Th2/Th17 bias (Th1: IL-2, IFN $_7$ , TNF $_\alpha$ ; Th2: IL4, IL-5, IL-10; Th17: IL-17a). Antigen specific T-regs will also be assayed as described  $^{72}$ .

We will also assay supernatants of PBMC, and of immune cells infiltrating the VSME, cultured 2 and 5 days with the 7 long peptides to define secreted cytokines and chemokines representative of the whole cell population. We anticipate that the long peptides will induce Tc1 and Th1 dominant responses, with a high proportion of memory phenotype after several vaccines.

Peripheral blood mononuclear cells (PBMC) and vaccine-site inflammatory cells from participants in this clinical trial may also be evaluated for CD4 T cell reactivity, using a 3H-thymidine uptake assay, CFSE dilution or other assays as summarized above.

Responses to the tetanus helper peptide will be assayed as well as responses to the 30-mer melanoma peptides and 15-mer pools comprising those peptides. Either or both of two peptides will be used as negative controls for CD4+ T cell responses: one being the PADRE peptide (aK(X)VAAWTLKAa), where X = L-cyclohexylalanine  $^{73;74}$ .

## 8.5 Antibody responses

Antibody responses to 30 mer peptides (and to pools of 15-mer peptides) will be measured by ELISA assay using methods described by Sabbatini et al .

### 8.6 Evaluation of tumor

Tumor tissue collected prior to enrollment or at the time of progression will be evaluated by routine histology and immunohistochemistry. In addition, *in vitro* evaluations of tumor tissue and tumor infiltrating lymphocytes may be completed.

# 9.0 STATISTICAL CONSIDERATIONS

This is an open-label, Phase I/II study evaluating the safety and immunogenicity of a long peptide vaccine (LPV7) + TLR for resected stage IIB – IV melanoma. There are two parts to the study.

For Part 1, the trial was designed to find the range of optimal combination therapies, defined as combinations with high immunologic response and an acceptable level of toxicity. The primary outcomes included the frequency of treatment related dose limiting toxicities (DLTs) and frequency of immunologic response. For Part 2, the goal is to obtain preliminary safety and immunogenicity data on the optimal combination identified in Part 1 when administered in the same skin site for all 6 vaccines (same site vaccination).

For part 2, the vaccine regimen is selected based on available data from Part 1, in which the strongest immune responses were observed in participants enrolled on Arms E and G (Table 1A). Resiquimod is no longer available; so the regimen for Arm G is not currently feasible. Also, the total enrollment on Arm E is larger (15 vs 6) so that outcomes from Part 2 will be evaluable in a similar sample size as for Part 1, Arm E. This group will be called Study Arm E2.

